3.0 OBJECTIVES AND ENDPOINTS

Table 2 Study Objectives and Endpoints

Objectives	Endpoints
Primary	

 To assess the efficacy of ATI-450 in patients with moderate to severe HS 	
 Change from Baseline in inflammatory nodule/abscess count at Week 12
Secondary	
 Percentage of patients achieving HiSCR at Week 12. 
HiSCR is defined as at least a 50% reduction from Baseline in the total abscess and inflammatory nodule (AN) count, with no increase in abscess or draining fistula counts.
 
 Change from Baseline in IHS-4 over time for the 12-week treatment period. Percentage of patients achieving at least a 30% reduction and at least 1 unit reduction from Baseline in the numerical rating scale (NRS30) in Patient's Global Assessment of Skin Pain at Week 12 among patients with Baseline NRS ≥ 3. 
NRS30 is evaluated based on worst skin pain in a 24-hour recall period (maximal daily pain).
 
 Change from Baseline in Hidradenitis Suppurativa-Physician Global Assessment (HS-PGA) over time for the 12-week treatment period. Change from Baseline in Dermatology Life Quality Index (DLQI) over time for the 12-week treatment period. 
The DLQI is a 10-item validated questionnaire used to assess the impact of HS disease symptoms and treatment on quality of life (QoL). It consists of 10 questions evaluating impact of skin diseases on different aspects of a patient's QoL over the prior week, including symptoms and feelings, daily activities, leisure, work or school, personal relationships, and the side effects of treatment.

Objectives	Endpoints
Secondary (continued)	
	
 Change from Baseline in Hurley Stage over time for the 12-week treatment period. Incidence of adverse events (AEs), serious AEs (SAEs), laboratory value abnormalities, electrocardiogram (ECG) abnormalities, vital signs abnormalities

 To assess the PK of ATI-450 in patients with moderate to severe HS 	
 Trough ATI-450 and metabolite (CDD-2164) concentrations at clinic visits. On Day 1, 8, and 85 trough and 2-hour post dose will be collected.
Exploratory	

 To assess the pharmacodynamics (PD) of ATI-450 in patients with moderate to severe HS 	 

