8.2.4 Clinical Safety Laboratory Assessments

See [Appendix 3](#) for the list of clinical laboratory tests to be performed and the SoA ([Table 1](#)) for the timing and frequency.

The Investigator must review the laboratory report, document this review, and record any clinically relevant changes occurring during the study in the AE Section of the eCRF. The laboratory reports must be filed with the source documents. Clinically significant abnormal laboratory findings are those that are not associated with the underlying disease, unless judged by the Investigator to be more severe than expected for the patient's condition.

See [Section 7.0](#) for discontinuation criteria based on abnormal liver function tests, neutrophil values, CK values, or positive SARS-CoV-2 test.

All laboratory tests with values considered clinically significantly abnormal during participation in the study or within 30 days (+7 days) after the last dose of study treatment should be repeated until the values return to normal or Baseline or are no longer considered clinically significant by the Investigator or Medical Monitor.

- If such values do not return to normal/Baseline within a period of time judged reasonable by the Investigator, the etiology should be identified and the Medical Monitor notified.
- All protocol-required laboratory assessments, as defined in [Appendix 3](#), must be conducted in accordance with the Laboratory Manual and the SoA ([Table 1](#)).
- If laboratory values from non-protocol specified laboratory assessments performed at the institution's local laboratory require a change in patient management or are considered clinically significant by the Investigator (eg, SAE or AE), then the results must be recorded in the eCRF.
- Serum potassium levels < 3.8 mmol/L will be treated and repeated as will serum magnesium levels < LLN.

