### **3.3.9. Presentations by Study Visit**

Scheduled and unscheduled assessments collected from Visit 1 through Visit 8 for all efficacy assessments and safety assessments (labs, vital signs, and ECG) will be assigned to an analysis visit window using the study day ranges described in [Table 1](#) and [Table 2](#). All study days up to and

---

including Day 1 are in the baseline-eligible analysis visit window. The last non-missing assessment in the baseline-eligible analysis visit window will be used in any summaries that present the baseline results with the exception of ECG interpretation where the best result from the triplicate values will be chosen. Day 1 post-dose ECG, PK and vital signs assessments will be analyzed as collected. Day 8 ECG assessments, Day 8 and 85 PK assessments, and Day 8, 15, 29, 43, 57 and 85 vital sign assessments will be windowed per Table 2, then each time point will be analyzed as collected. For all other assessments, for post-baseline analysis windows, if multiple assessments occur within a given analysis visit window, the result closest to the target study day, regardless of whether scheduled or unscheduled, will be used for summary presentations. If two measurements have the same distance to the target study day, the first assessment will be used in the summary presentations with the exception of ECG interpretation where the worst result from the triplicate values for the given visit and timepoint will be used. All assessments will be presented in the listings. In addition to the analysis visits indicated in Table 1 and Table 2, for patients who prematurely discontinue the study, data collected during the withdrawal visit will be used as an EOS assessment for these patients. The EOS assessment will be included in safety analyses.

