**Table 2: Visit Windows Assessments Other than DLQI**

CRF Visit	Target Study Day	Analysis Visit	Study Day Range
Visit 1	-28 to -1	Baseline	<1 or Day 1 pre-dose
Visit 2	1		
Visit 3	8	Week 1	[2 – 11]
Visit 4	15	Week 2	[12 – 21]
Visit 5	29	Week 4	[22 – 35]
Visit 6	43	Week 6	[36 – 49]
Visit 7	57	Week 8	[50 – 70]
Visit 8(EoT/ET)	85	Week 12	[71 – 98]
Visit 9(EoS)	30 days after last dose	EOS	Latest assessment after the EoT/ET

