### **5.5.2. Clinical Laboratory Assessments and Vital Signs**

Laboratory data (hematology, serum chemistry, coagulation, FSH and urinalysis) will be converted to Système International (SI) units for reporting and processing purposes.

Descriptive summaries of absolute values of quantitative clinical laboratory results and their change from baseline values will be presented by analysis visit and treatment group. Observed values of categorical urinalysis data will be displayed with frequencies and percentages. All laboratory data will be listed for individual patients.

Treatment-emergent abnormal laboratory assessments will be based on the lab provided normal ranges. If the baseline laboratory assessment is normal and shifts to Low or High post-baseline, then the laboratory value is considered a TE abnormal laboratory value. If the baseline laboratory assessment is Low and shifts to High post-baseline or the baseline laboratory assessment is High and shifts to Low post-baseline, then the laboratory value is considered a TE abnormal laboratory

value. For each protocol specified lab test, the number and percent of patients reporting a TE abnormal lab will be reported.

For CK, Absolute Neutrophils, ALT, AST, and Bilirubin, laboratory abnormalities will be graded via the Common Terminology Criteria for Adverse Event (CTCAE) version 5.0. A summary of treatment-emergent laboratory toxicities for the indicated laboratory results by maximum CTCAE toxicity grades will be reported.

All laboratory summaries will be limited to the tests specified in the protocol.

Descriptive summaries of vital signs, weight, and BMI and their change from baseline will be presented by study visit and treatment group and all vital signs will be listed.

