#### **5.5.3. Other Safety Analyses**

ECG measurements will include heart rate, QT interval, Fredericia-corrected QT interval (QTcF), PR interval, and QRS interval. Triplicate ECG values will be obtained at each time point. Summary tables will present the average of the triplicate ECG results. ECG results and their change from baseline values will be summarized descriptively by treatment group at each scheduled evaluation and all ECG data will be listed. Proportion of patients with abnormal ECG interpretations will be summarized at each study visit and by treatment group for both investigator and central interpretation. Proportion of patients who meet each of the following criteria based on triplicate averages from International Conference on Harmonization Guideline E14 “Clinical Evaluation of QT/QTc Interval Prolongation and Proarrhythmic Potential for Non-Antiarrhythmic Drugs” (October 2005) for QT and corrected QT intervals will be summarized across treatment groups:

- QTcF >450 msec
- QTcF >480 msec
- QTcF >500 msec
- QTcF increases from baseline by >30 msec
- QTcF increases from baseline by >60 msec

The above summaries will be repeated for QT.

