## **Section 14.3 Safety**

Table 14.3.1.1 Overall Summary of Adverse Events, Safety Population

Table 14.3.1.2 Treatment-Emergent Adverse Events by System Organ Classification, Preferred Term and Greatest Severity, Safety Population

Table 14.3.1.3 Treatment-Emergent Adverse Events by System Organ Classification and Preferred Term, Safety Population

Table 14.3.1.4 Treatment-Emergent Serious Adverse Events by SOC and PT, Safety Population

Table 14.3.1.5 Treatment-Emergent Adverse Events Related to Study Drug by SOC and PT, Safety Population

Table 14.3.1.6 Treatment-Emergent Adverse Events Leading to Discontinuation of Study Drug by SOC and PT, Safety Population

Table 14.3.1.7 Study Drug Related Treatment-Emergent Adverse Events Leading to Discontinuation of Study Drug by SOC and PT, Safety Population

Table 14.3.1.8 Adverse Events of Special Interest (AESI) by SOC and PT, Safety Population

Table 14.3.1.9 Summary of Most Frequent Treatment Emergent Adverse Events by Preferred Term, Safety Population

Table 14.3.4.1.1 Summary of Hematology and Coagulation Results and Change from Baseline by Analysis Visit, Safety Population

Table 14.3.4.1.2 Summary of Serum Chemistry Results and Change from Baseline by Analysis Visit, Safety Population

Table 14.3.4.1.3 Summary of Urinalysis Results and Change from Baseline by Analysis Visit, Safety Population

Table 14.3.4.2.1 Summary of Treatment-Emergent Abnormal Hematology and Coagulation by Analysis Visit Safety Population

Table 14.3.4.2.2 Summary of Treatment-Emergent Abnormal Serum Chemistry by Analysis Visit, Safety Population

Table 14.3.4.2.3 Summary of Treatment-Emergent Abnormal Urinalysis by Analysis Visit, Safety Population

Table 14.3.4.4 Summary of Laboratory Results by CTCAE Toxicity Grades for CK, Absolute Neutrophils, ALT, AST, and Bilirubin, Safety Population

---

Table 14.3.5.1 Summary of Vital Signs and Change from Baseline by Analysis Visit, Safety Population

Table 14.3.5.2.1 Summary of ECG Results and Change from Baseline by Analysis Visit, Safety Population

Table 14.3.5.2.2.1 Proportion of Patients with Abnormal Investigator ECG Interpretations by Analysis Visit, Safety Population

Table 14.3.5.2.2.2 Proportion of Patients with Abnormal Central ECG Interpretations by Analysis Visit, Safety Population

Table 14.3.5.2.3 Proportion of Patients with Noteworthy QT Changes by Analysis Visit, Safety Population

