Table 14.3.5.2.4 Proportion of Patients with Noteworthy QTcF Changes by Analysis Visit, Safety Population

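### SAP 5.5.2 and 5.5.3 promise patient-level counts of laboratory and QT/QTcF abnormalities, but the proposed tables are by analysis visit and no visible text adds an any-time count

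*SAP*

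**What the plan says.** The protocol's secondary safety endpoint (section 3.0) is the incidence of adverse events and of "laboratory value abnormalities, electrocardiogram (ECG) abnormalities, vital signs abnormalities".

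SAP 5.5.2 turns the laboratory part into a patient count: "For each protocol specified lab test, the number and percent of patients reporting a TE abnormal lab will be reported". SAP 5.5.3 does the same for the QT and QTcF thresholds: "Proportion of patients who meet each of the following criteria based on triplicate averages". Neither sentence mentions a visit.

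The proposed tables in SAP section 9 do. Tables 14.3.4.2.1 to 14.3.4.2.3 follow the pattern "Summary of Treatment-Emergent Abnormal Serum Chemistry by Analysis Visit, Safety Population". Table 14.3.5.2.4 is "Proportion of Patients with Noteworthy QTcF Changes by Analysis Visit, Safety Population", and Table 14.3.5.2.3 is its QT counterpart.

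SAP 3.3.9 governs which value enters a visit row. When several fall in one window, "the result closest to the target study day, regardless of whether scheduled or unscheduled, will be used for summary presentations"; a tie goes to the earlier one. Day 1 post-dose ECGs and the Day 8 ECG time points are exempt. For the end-of-study row, Table 2 takes the "Latest assessment after the EoT/ET". Protocol 8.2.4 says that clinically significantly abnormal laboratory tests seen on study or found "within 30 days (+7 days) after the last dose of study treatment should be repeated until the values return to normal or Baseline"; repeating also ends once the result is not judged clinically significant any more.

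For ECG interpretation (normal or abnormal), SAP 3.3.9 takes the best of the three tracings at baseline and the worst of the three afterwards.

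**The concern.** An incidence question asks how many patients per arm were ever abnormal. Rows by visit answer a different question, and they cannot be added, because the same patient may appear in several rows or only one.

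The selection rule adds to this. Unscheduled visits are allowed for repeat laboratory draws and safety follow-up, so their values may be the ones that carry a signal. A nearest-day rule leaves most of them out of the row whenever the scheduled visit also took place.

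At stake are safety tables that a reader would naturally consult for the number of patients crossing a QTcF threshold, or with, say, an abnormal potassium or magnesium. The protocol itself gives these measures weight: baseline QTcF above 450 msec and uncontrolled low potassium or magnesium are exclusions.

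**Working it through.** The plan states no expected abnormality rate, so there is no figure of its own to reproduce. The check compares text with table titles, then applies simple bounds.

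**1. Text against titles.** The SAP distinguishes the two kinds of summary elsewhere. In 5.5.3, abnormal ECG interpretations are promised visit by visit; the QT/QTcF criteria are not. For creatine kinase, neutrophils, ALT, AST and bilirubin, 5.5.2 asks for the maximum CTCAE grade, 3.3.8 defines toxicity over any post-baseline visit, and Table 14.3.4.4 carries no visit in its title. The treatment-emergent abnormality and QT/QTcF tables have no such specification.

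**2. What visit rows can tell.** If each of n rows shows x patients, the number ever abnormal among the selected values lies between x (always the same patients) and n·x (always different ones). Inputs: 45 patients per arm (SAP 3.1) and an assumed x = 2.

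- Laboratory tests: n = 7 (Weeks 1, 2, 4, 6, 8, 12 and end of study). Range 2 to 7 × 2 = 14 of 45, or 4% to 31%.
- ECGs in fasted patients: n = 8 (Day 1 at 2 h; Day 8 pre-dose and 2 h; Weeks 2, 4, 6, 8, 12). Range 2 to 8 × 2 = 16 of 45, or 4% to 36%.

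Patients abnormal only on a value that was not selected would come on top.

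**3. What the nearest-day rule selects.** Let T be the target day and the scheduled visit fall on T−1, T or T+1, the permitted window. An unscheduled value on day d is taken only if it is nearer to T than the visit, or equally near and not later. No value more than one day from T can then be selected.

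- Scheduled Day 57 normal, unscheduled Day 64 abnormal: both lie in the Week 8 window (Days 50 to 70), and the row shows normal.
- Scheduled Day 56 abnormal, repeat on Day 57 normal: the row shows normal. A later repeat displaces an abnormal scheduled value only in this pattern (visit one day early, repeat on the target day).
- If the scheduled visit is missed, an unscheduled value can be selected.

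**4. End of study.** If a repeat drawn after Visit 9 counts as an assessment after EoT/ET, the latest-value rule puts the resolved repeat in the row in place of the abnormal Visit 9 value. This concerns laboratory tests; no ECG is scheduled at Visit 9.

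**5. What is covered elsewhere.**

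| Measure | Other patient-level route |
|---|---|
| QTcF above 500 or change above 60 msec | Adverse event of special interest |
| CK, neutrophils, ALT, AST, bilirubin | Maximum-grade table; CK and neutrophils also as events of special interest |
| Clinically relevant laboratory changes, clinically significant ECGs | Adverse event recording (Protocol 8.2.3, 8.2.4) |
| QT criteria; QTcF above 450, above 480, change above 30 msec | Listings only, unless recorded as an adverse event |
| Other laboratory tests | Listings only, unless recorded as an adverse event |

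**6. ECG interpretation (secondary).** With per-tracing abnormal probability q and correlation r between the three readings, worst-of-three minus best-of-three is 3q(1−q)(1−r). Both inputs are assumed. At q = 0.03, r = 0.9: 3 × 0.03 × 0.97 × 0.1 = 0.9 points (0.4 of 45 patients). At q = 0.10, r = 0.8: 3 × 0.10 × 0.90 × 0.2 = 5.4 points (2.4 of 45). If the three readings always agree, the difference is zero.

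**The case against.** The strongest reply is that SAP section 9 lists only proposed titles. No shells are available, a table by visit can still carry an overall row, and the method text is already at patient level. SAP 3.3.7 and most of SAP section 6 are redacted. This stands as a limit: the point is conditional on the tables being built as titled and rests on the visible text.

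Next, the nearest-day rule is an ordinary convention for by-visit summaries. That is right, and the rule should stay. A reader might infer that the rule itself is an error; it is only the wrong feed for an incidence count.

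A reader might also infer that the number ever abnormal is lost or hidden. It is not. All assessments are listed, there is a separate listing of laboratory abnormalities, and Protocol 9.4.2 promises no more than listings of out-of-range laboratory data and descriptive ECG summaries. The count is missing from the planned tables, not from the data.

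On the end-of-study row, it is tempting to say that an abnormal Visit 9 value is replaced. Table 2 can be read that way, but SAP 3.3.9 assigns scheduled and unscheduled values to windows only through Visit 8, and Table 2 ties the row to Visit 9. The documents do not settle whether a later repeat enters. Whether events first found at Visit 9 count as treatment-emergent is a separate question of adverse event definition and forms no part of this point.

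Finally, the ECG interpretation rule is pre-specified and deliberate, as the revision history shows, and it applies to both arms. A reader might infer bias in the treatment comparison or in the QT/QTcF criteria. Neither follows: the arms are handled alike, and the criteria use triplicate averages.

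**Conclusion.** The point holds as a minor mismatch between promised counts and proposed tables. If Tables 14.3.4.2.1 to 14.3.4.2.3, 14.3.5.2.3 and 14.3.5.2.4 are built as titled, they will not give the number of patients ever abnormal. Nor will most off-target unscheduled values enter them when the scheduled visit is held. The gap is confined to the last two rows of the coverage table above.

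Its size in patients cannot be derived from the documents. The ranges of 2 to 14 and 2 to 16 of 45 show only that visit rows do not determine the count; they rest on an assumed 2 patients per row and are not a forecast.

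The best-then-worst triplicate rule is a secondary matter. It inflates the within-arm rise in abnormal ECG interpretations by an amount that depends on unknown reading agreement, so that rise should not be read as a change on treatment.

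**What to change.** - Keep the nearest-day rule for by-visit descriptive summaries.
- Add an any-post-baseline row to the treatment-emergent abnormal laboratory tables and the QT and QTcF tables. Use all scheduled and unscheduled post-baseline values, including those after EoT/ET, with triplicate averages for QT and QTcF.
- State that Table 14.3.4.4 uses all post-baseline values, including any not selected for a window.
- Secondary: use the same triplicate rule for ECG interpretation at baseline and afterwards.

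The cost is a few sentences in the SAP and a few table rows, with no new data. Some displayed abnormality rates will be higher, and so will the baseline rate of abnormal ECG interpretations if worst-of-three is chosen throughout.

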**Table 1: Visit Windows for DLQI**

CRF Visit	Target Study Day	Analysis Visit	Study Day Range
Visit 2	1	Baseline	$\leq 1$
Visit 5	29	Week 4	[2 – 42]
Visit 7	57	Week 8	[43 – 70]
Visit 8(EoT/ET)	85	Week 12	[71 – 98]

**Table 2: Visit Windows Assessments Other than DLQI**

CRF Visit	Target Study Day	Analysis Visit	Study Day Range
Visit 1	-28 to -1	Baseline	<1 or Day 1 pre-dose
Visit 2	1		
Visit 3	8	Week 1	[2 – 11]
Visit 4	15	Week 2	[12 – 21]
Visit 5	29	Week 4	[22 – 35]
Visit 6	43	Week 6	[36 – 49]
Visit 7	57	Week 8	[50 – 70]
Visit 8(EoT/ET)	85	Week 12	[71 – 98]
Visit 9(EoS)	30 days after last dose	EOS	Latest assessment after the EoT/ET

### **3.4. TIMING OF ANALYSES**

When all patients have completed study ATI-450-HS-201 or terminated early from the study and the database has been locked, the analyses will be performed according to this SAP. No interim analysis is planned for this study.

## **4. ANALYSIS POPULATIONS**

The populations for analysis will include the full analysis set population (FAS), the per-protocol (PP) population, the safety population and the PK Population.

### **4.1. FULL ANALYSIS SET (FAS) POPULATION**

All patients who have been randomized and administered at least 1 dose of study treatment. The efficacy analyses will be conducted on the FAS population as randomized.

### **4.2. PER PROTOCOL (PP) POPULATION**

All randomized patients who remain on study drug and complete their assessments for the Day 85 visit and do not have major protocol deviations that could impact efficacy.

Patients are considered to have completed their Day 85 assessments if the AN count is recorded in the Week 12 analysis visit window. Protocol deviations and violations will be tracked as part of clinical monitoring and clinically evaluated by the sponsor as major or minor. Determination of protocol deviations that could impact efficacy will be conducted in a blinded manner by the sponsor prior to database lock.

### **4.3. SAFETY POPULATION**

All patients randomly assigned to study treatment and who take at least 1 dose of study treatment. Patients will be analyzed according to the treatment they received.

### **4.4. PHARMACOKINETIC (PK) POPULATION**

All patients randomly assigned to study treatment, take at least 1 dose of study treatment and have at least 1 evaluable PK assay will be included in the PK population, even if the results are below the limit of quantification (BLQ).

## **5. STATISTICAL METHODS**

Descriptive statistical methods will be used to summarize the data from this study, with hypothesis testing performed for the primary and secondary efficacy endpoints. Unless stated otherwise, the term “descriptive statistics” refers to number of patients, mean, median, standard deviation, minimum, and maximum for continuous data, and frequencies and percentages for categorical data. For categorical variables, the denominator of percentages will be the number of patients with a

---

non-missing value at the visit and/or the scheduled time point. If a different denominator is used, this will be identified in the summary table.

All data collected during the study will be included in data listings. Unless otherwise noted, the data will be sorted first by treatment group, subject number, and then by date within each subject number. Assessments indicated as 'Not Done' will not be included in the listings.

The term 'treatment group' refers to all patients on the same dosing regimen. There will be two treatment groups in this study: Placebo BID and ATI-450 50mg BID.

All statistical testing will be one-sided and will be performed using a significance (alpha) level of 0.05 unless otherwise stated. P-values will be presented to three decimal places. For the efficacy endpoints, the ATI-450 treatment group will be tested versus Placebo via statistical inference.

The statistical analyses will be conducted with the SAS® software package version 9.4 or higher. All analyses will be subject to formal verification procedures. Specifically, results will be independently verified by a second programmer or statistician prior to issuance of the draft statistical report. All documents will be reviewed by the lead statistician to ensure accuracy and consistency.

